### 7.3 Efficacy Analysis Set

The efficacy analysis set will be used for secondary endpoints. The efficacy analysis set includes all enrolled subjects in Study 20140159 who received at least one dose of cinacalcet during Study 20140159 and have at least one assessment

after Study Day 1. Subjects will be analyzed according to the treatment received in the parent studies and overall.

**7.4 Study 20130356 SOC Set**

The Study 20130356 SOC set will be used for secondary endpoints that analyze subjects from Study 20130356 SOC arm only. The Study 20130356 SOC set includes all Study 20140159 enrolled subjects from Study 20130356 who did not receive cinacalcet prior to Study Day 1 of 20140159 and received at least one dose of cinacalcet in Study 20140159 and have at least one assessment after Study Day 1 of 20140159.

**7.5 Per Protocol Set for Study 20140159 Only (for interim and final analyses)**

The Per Protocol Set for Study 20140159 only is defined as all **enrolled** subjects who **do not have significant deviations from the protocol (as assessed by IPD)**, or **missing > 2 doses within any dosing week or ≥2 documented overdoses within a dosing week**.

For each secondary endpoint that requires sensitivity analysis using per protocol set, a subset of the Per Protocol Set for Study 20140159 only who has at least one desired lab measurement during the corresponding evaluation period will be used.

**7.6 Per Protocol Set for Combined 20130356, 20110100 and 20140159 Studies (for final analysis only)**

The Per Protocol Set for combined 20130356, 20110100 and 20140159 studies is defined as all Study 20140159 enrolled subjects who **do not have significant deviations from the protocols of parent studies and Study 20140159 (as assessed by IPD)** or **non-compliance as defined for each study specifically**.

For each secondary endpoint that requires sensitivity analysis using per protocol set, a subset of the Per Protocol Set for Combined 20130356, 20110100 and 20140159 Studies who has at least one corresponding lab measurement during the corresponding evaluation period will be used.

### 7.7 Subgroup Analyses

The following characteristics **may** be used in the subgroup analyses planned for the primary, secondary **and safety** endpoints:

baseline age group in parent studies (6 to < 12 years old and 12 to < 18 years old for Study 20130356; 28 days to < 2 years old and 2 to < 6 years for Study 20110100)

gender (male and female)

race (black, white and other). If any category has **≤ 4 subjects**, the category will be pooled together with other category for summary purposes.

Tanner stage (1 and >1)

### 8. Interim Analysis and Early Stopping Guidelines

An interim analysis will be performed to support the sNDA for the pediatric indication. The scope of this interim analysis will be specified in **section 10** of this SAP. Additional interim analyses may be performed if necessary to support regulatory inquiries and the SAP may be amended to reflect the additional analyses. There are no plans to change the conduct of the study based on the interim analysis results.

There is no formal statistical testing. The analysis for all endpoints will be descriptive in nature.

### 9. Data Screening and Acceptance

#### 9.1 General Principles

The objective of the data screening is to assess the quantity, quality and statistical characteristics of the data relative to the requirements of the planned analyses.

#### 9.2 Data Handling and Electronic Transfer of Data

Amgen's Clinical Data Management department will provide all data to be used in the planned analyses. This study will use the RAVE database and non-CTDB database.

#### 9.3 Handling of Missing and Incomplete Data

##### 9.3.1 Examination of the Missing Data

Missing data frequency and pattern for any of the following key variables will be reviewed. The potential impact of these missing values on the planned analysis will be evaluated.

###### 1. Subject Identification Data

subject identification number

date of birth

race  
ethnicity  
sex  
center/site number  
country

2. Dates and Times

informed consent date  
enrollment date  
end of study date

3. Safety Data

dates for onset of adverse events  
dates for resolution of adverse events (if not continuing at the end of the study)  
CTCAE v4 severity grading, relationship to treatment, seriousness, and action taken for adverse events

4. Efficacy Data

iPTH, corrected total serum calcium values, ionized calcium values, phosphorus values and dates of assessment

5. Investigational Product Administration

Daily planned IP (dose level, date, reason for dose change)  
Daily IP administration (dose level, date, reason for dose change/withheld)  
box ID numbers

**9.3.2 Handling of Missing Data**

**9.3.2.1 Missing Adverse Event date**

**For any listings, missing or incomplete dates will be listed as is.**

All missing dates (missing entirely or partially) of adverse events occurring after first dose of IP will be queried. **For adverse events with the question “Did event start before first dose of investigational product?” on the eCRF was answered as “Yes”, the missing adverse event start dates won’t be imputed.** All other missing adverse event start dates will be handled as described below:

**When the adverse event start year is available and the start day and month are missing, if the start year is the same as the year of Study Day 1, the start date will be set to date of Study Day 1, otherwise set to the 1st of January of the onset year.**

**When the start year and month are available and the start day is missing, if the start year and month are the same as the year and month of Study Day 1, the start date will be set to date of Study Day 1, otherwise the 1st of the month of the onset year.**

**If the entire start date is missing, it will be set to the date of Study Day 1**

#### **9.3.2.2 Other Missing Dates**

Partial/missing start dates for vitamin D, phosphate binders, calcium supplements, and growth hormone will be imputed using the **following** algorithm.

**If the start year is available and the start day and month are missing, the start date will be set to the 1st of January of the onset year.**

**If the start year and month are available and the start day is missing, the start date will be set to the 1st of the month of the onset year.**

**If the entire start date is missing, it will not be imputed.**

Partial/missing stop dates for the concomitant medications (not continuing at the end of the study) will be imputed using the following logic:

If the stop year is available and stop month and day are missing, the **stop date** will be reset to **31st of December** of the stop year.

If the stop year and month are available and the stop day is missing, the stop **date** will be set to the **last day** of the month of the **stop** year.

If the stop year and day are available and stop month is missing, the stop month will be set to **December** of the **stop** year.

If the stop month and day are available and stop year is missing, the stop year will be reset to the year of the **End of Study** date.

**If the entire stop date is missing, it will not be imputed.**

#### **9.4 Detection of Bias**

This study is an open label, single arm study. Some factors that may bias the results of the study include:

important protocol deviations likely to impact the analysis and interpretation of the efficacy endpoints

IP dosing compliance

the timing of and reasons for early withdrawal from treatment and from study

The incidence of these factors **as well as potential biases from the parent studies discussed in the parent studies SAPs** will be assessed. Important protocol deviations likely to impact the analysis and interpretation of the efficacy endpoints will be tabulated in the Clinical Study Report (CSR). If necessary, the incidence of the other factors will be reported as well.

#### **9.5 Outliers**

This is a descriptive study, all outliers that are not known errors will be included in the relevant analysis. Outliers that are confirmed to be errors that are discovered before the database lock will be corrected in the database by CDM. Any erroneous values discovered after the database lock will be noted in the CSR.

#### **9.6 Distributional Characteristics**

There is no distributional assumption being made due to the descriptive nature of the analysis. Both mean and median will be presented for continuous outcomes.

#### **9.7 Validation of Statistical Analyses**

Programs will be developed and maintained, and output will be verified in accordance with current risk-based quality control procedures.

Tables, figures and listings will be produced with validated standard macro programs where standard macros can produce the specified outputs.

The production environment for statistical analyses consists of Amgen-supported versions of statistical analysis software, for example the SAS System version 9.2 or later and Qualified R.

### **10. Statistical Methods of Analysis**

#### **10.1 General Principles**

There is no formal statistical testing for this study. The analysis of all endpoints will be descriptive in nature.

Descriptive statistics will be used to summarize data for continuous variables (including n, mean, standard deviation (SD), standard error (SE), median, 25th (Q1) and 75th (Q3) percentiles, minimum and maximum values, and corresponding 2-sided 95% CI, where applicable.) For categorical variables, the number and percentage of subjects in each category, will be reported. Graphical presentation may be provided for selected variables.

**The laboratory data collected more than 7 days after the last dose of IP will be excluded for the efficacy analyses.**

**For the interim analysis supporting pediatric sNDA, only data from the 20140159 study before interim data cutoff date will be analyzed according to the actual treatment received from the parent study and overall.**

**For the final analysis, final efficacy and safety data from Study 20140159 will be analyzed. In addition, cumulative data combining the parent studies (20130356 and 20110100) and Study 20140159 will also be summarized.**

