# 3. EXPERIMENTAL PLAN

#### 3.1 Study Design

This is a phase 3, 32-week, multicenter, single-arm, extension study designed to characterize the long-term safety and tolerability of cinacalcet in pediatric subjects. Subjects will remain on cinacalcet treatment for 28 weeks after enrollment or until the time of renal transplant or parathyroidectomy, whichever occurs first. The treatment period is followed by a 4-week safety follow-up period.

The overall study design is described by a **Study Design and Treatment Schema** at the end of the protocol synopsis section.

The study endpoints are defined in Section 10.1.1.

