# 7.2.5 Early Termination

Subjects who discontinue participation in the study prior to week 28 will be asked to complete an early termination visit and should have all EOIP and EOS evaluations performed as outlined in the Schedule of Assessments and in Sections 7.2.4 and 7.2.6.

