# 8.2 Reasons for Removal From Study

# 8.2.1 Reasons for Removal From Treatment

Reasons for removal from protocol-required IP(s) or procedural assessments include any of the following:

- subject request
- safety concern (eg, due to an adverse event, protocol deviation, non-compliance, requirement for alternative therapy, pregnancy)
- protocol-specified criteria (eg, renal transplant, parathyroidectomy)
- death
- lost to follow-up
- decision by sponsor (other than subject request, safety concern, lost to follow-up)

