## 3. Study Overview

### 3.1 Study Design

This is a phase 3, 32-week, multicenter, single-arm, extension study designed to characterize the long-term safety and tolerability of cinacalcet in pediatric subjects.

**Subjects will remain on cinacalcet treatment for 28 weeks after enrollment from parent studies 20110100 or 20130356, or until the time of renal transplant or parathyroidectomy, whichever occurs first. The treatment period is followed by a 4-week safety follow-up period.**

The overall study design is described by a study schema at the end of the protocol synopsis section.

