**Analysis window for iPTH**

Study Visit	Target Day	Study Day	Interval (days)
Baseline	1	<= 1	N/A
Week 3	22	2-36	35
Week 7	50	37-64	28
Week 11	78	65-92	28
Week 15	106	93-120	28
Week 19	134	121-148	28
Week 23	162	149-176	28
Week 28	197	177-211	35
Week 32	225	≥212	N/A

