**Analysis window for vital signs and all other labs.**

Study Visit	Target Day	Study Day	Interval (days)
Baseline	1	≤ 1	N/A
Week 3	22	2-36	35
Week 7	50	37-64	28
Week 11	78	65-92	28
Week 15	106	93-120	28
Week 19	134	121-148	28
Week 23	162	149-176	28
Week 27	190	177 – 194	18
Week 28	197	195 – 211	17
Week 32	225	≥212	N/A

If there is more than one observation in a visit window, use the value collected closest to the target day. If multiple observations are equally close to the target day, use the later value.

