#### Study20140159only

Proportion of subjects achieving the secondary endpoints of  $\geq 30\%$  reduction in iPTH from study baseline to mean value during weeks 11 and 15 will be reported with 95% CI based on 20130356 SOC Set. Subjects who have no iPTH values during weeks 11 or 15 will be considered non-responders.

Proportion of subjects achieving the secondary endpoints of  $\geq 30\%$  reduction in iPTH from study baseline to mean value during weeks 23 and 28 will be reported with 95% CI based on 20130356 SOC Set. For subjects who do not have a iPTH value during weeks 23 and 28, the mean of the last two available post-baseline values in the dose-titration phase will be used. If only one post-baseline value is available, this single value will be used. If no post-baseline value is available, the subject is considered a non-responder.

Summary statistics will be provided for percent change from study baseline to mean iPTH during weeks 23 and 28 based on 20130356 SOC Set, and change in corrected total calcium and change in serum phosphorus from study baseline to mean value during weeks 23 and 28 based on efficacy analysis set by treatment group in the parent studies. For subjects who are missing the efficacy measurement during weeks 23 to 28, the mean of the last two available post-baseline values in the dose titration phase will be used. If only one post-baseline value is available, this single value will be used. If no post-baseline value is available, the subject will be excluded from the analysis.

Proportion of subjects who achieve a mean iPTH value  $\leq 300$  pg/mL during weeks 23 and 28 will be provided based on efficacy analysis set by the treatment group in parent study with 95% CI. For subjects who do not have an iPTH value during weeks 23 and 28, the mean of the last two available post-baseline values in the dose-titration phase will be used. If only one post-baseline value is available, this single value will be used. If no post-baseline value is available, the subject is considered a non-responder.

**Summary statistics will be provided for serum cCa and phosphorus values at study baseline, week 11, and week 28 for all efficacy analysis set subjects.**

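### The efficacy laboratory cut runs from the last dose only, so an iPTH value drawn shortly after parathyroidectomy or renal transplant can be scored as a cinacalcet response

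*SAP*

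**What the plan says.** **When treatment ends.** Protocol 3.1: "Subjects will remain on cinacalcet treatment for 28 weeks after enrollment or until the time of renal transplant or parathyroidectomy, whichever occurs first". SAP 3.1 repeats this, and the SAP does not mention either procedure again. Protocol 8.2.1 lists both as reasons for removal from treatment; the removal-from-study list in 8.2.2 contains neither.

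**Which values are kept.** The only time cut is in SAP 10.1: "The laboratory data collected more than 7 days after the last dose of IP will be excluded for the efficacy analyses".

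**Where a post-procedure value could come from.** A child who stays on study has iPTH drawn at weeks 3, 7, 11, 15, 19, 23, 28 and 32 (Protocol Table 4). A child who leaves the study before week 28 is asked to attend an early termination visit and "should have all EOIP and EOS evaluations performed as outlined in the Schedule of Assessments" (Protocol 7.2.5). Those evaluations include iPTH, corrected calcium and phosphorus (7.2.4 and 7.2.6).

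**How values reach an endpoint.** SAP 6.2 assigns values to visits by study day alone, and "If there is more than one observation in a visit window, use the value collected closest to the target day". Under SAP 10.6.1, a child is a non-responder at weeks 11/15 only for lack of values. At weeks 23/28, if values are missing, "the mean of the last two available post-baseline values in the dose-titration phase will be used". SAP 6.1 ends that phase at week 24.

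**The concern.** The secondary objective is the effect of cinacalcet on laboratory markers of mineral and bone disease. A value drawn after the parathyroid glands have been operated on, or after a new kidney has been placed, reflects that procedure as well as the drug. The clock in SAP 10.1 starts at the last dose, and the last dose may be given up to the procedure. The rule therefore lets some of these values through.

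For iPTH the error favours the drug: a surgical fall can count as a reduction of at least 30%, or as a mean of 300 pg/mL or less. The calcium and phosphorus change summaries can pick up the same contamination. The endpoints that use Study 20140159 data alone also enter the interim analysis supporting the sNDA, and the responder denominators are small.

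**Working it through.** **Denominator.** SAP 3.2 plans 48 + 30 = 78 children, which reproduces its stated 78. Study 20130356 randomises 1:1 (Protocol 2.5.1), so the former standard-of-care set has at most about 48/2 = 24.

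**Windows for iPTH (SAP 6.2).** Week 11 is days 65–92, week 15 days 93–120, week 19 days 121–148, week 23 days 149–176 and week 28 days 177–211.

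**Last-dose days that can feed an endpoint directly.** Weeks 11/15: from 65 − 7 = day 58 to 120 − 1 = day 119. Weeks 23/28: from 149 − 7 = day 142 to the end of treatment, about day 197. The last-two-values rule adds earlier days (case D).

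**The SAP rules applied to hypothetical children.** Assumptions, not document figures: baseline iPTH 1000 pg/mL, no change on drug, 50 pg/mL after the procedure, last dose on the day of the procedure. A single value in a pair of weeks is taken to suffice.

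| Case | Procedure day / draw day | Values used as planned | Result as planned | Post-procedure value removed |
|---|---|---|---|---|
| A, weeks 11/15 | 70 / 75 | 50 | mean 50, responder | no value, non-responder |
| B, weeks 11/15 | 100 / 105 | 1000 and 50 | mean 525 (−47.5%), responder | mean 1000, non-responder |
| C, weeks 23/28 | 155 / 160 | 50 | mean 50, responder and ≤ 300 | last two values 1000 and 1000, neither met |
| D, weeks 23/28, last-two rule | 128 / 133 | 1000 and 50 | mean 525 (−47.5%), responder | mean 1000, non-responder |

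If both visits of a pair were required, A would be a non-responder. B and D would not change. C would pass to the last-two rule: (1000 + 50)/2 = 525, still a responder but above 300.

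**How large a fall is needed.** With baseline B and post-procedure value x:
- x alone: response if x ≤ 0.7B.
- x averaged with an unchanged value: (B + x)/2 ≤ 0.7B, so x ≤ 0.4B.
- A child who worsened on drug, with baseline 900 and last pre-operative value 1000: any x ≤ 2 × 0.7 × 900 − 1000 = 260 gives a response. At x = 50 the mean is 525 and (525 − 900)/900 = −41.7%.

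**Limits of the exposure.** In case A, a draw on day 78 (8 days after the last dose) is excluded and the child is a non-responder. If dosing stopped 5 days before surgery, only draws up to 7 − 5 = 2 days after it count. For a child who stays on study, if procedure timing is uniform between scheduled draws and the last dose is on the day of the procedure, a draw falls in the 7 days with chance 7/28 = 25% (7/35 = 20% between weeks 23 and 28).

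**Effect on the proportion.** One child moves it by 1/24 = 4.2 points. For example, 12/24 = 50.0% (exact 95% CI 29.1 to 70.9) becomes 13/24 = 54.2% (32.8 to 74.4). With an assumed 12 in the set the step is 1/12 = 8.3 points. With all 78 in the denominator it is 1/78 = 1.3 points.

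**The case against.** The strongest case against is that several things must coincide.

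- **The 7 days are not counted from surgery.** A reader might infer that every value within a week after surgery is kept. That is only the limiting case of dosing on the day of the procedure. This stands.
- **Surgery does not itself trigger a termination visit.** A reader might infer that early termination bloods always follow. Both procedures remove a child from treatment, not from study. The visit is requested only of children who leave the study, and no deadline places it within 7 days of the last dose. This stands; a scheduled draw is the other route.
- **The value must be selected.** A pre-operative value nearer the target day displaces it. For the combined-study weeks 23/28 endpoint, the last-two rule takes only values from protocol-specified visits. This stands, but cases A to D each satisfy the selection rules for the endpoints based on Study 20140159 alone.
- **Other analyses might catch it.** The weeks 11/15 completer analysis drops children who left before completing 15 weeks, but only at the final analysis. The weeks 23/28 completer analysis keeps anyone with one value. The per-protocol set removes important deviations and non-compliance, and a protocol-specified stop is not in itself either. Inverse probability weighting addresses missing values and does not remove observed ones. The nearest-two imputation admits unscheduled values. SAP 10.2 lists the time of and reason for withdrawal, which makes cases visible but does not correct the proportion. No listed analysis censors at the procedure.
- **The endpoints are secondary and descriptive.** This is true. There is no formal testing, the primary safety endpoint is untouched, and one child's shift is small beside the confidence interval.

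**Conclusion.** The gap is real but narrow. As written, the SAP can keep a post-procedure value as on-treatment efficacy data and so score a child with no drug response as an iPTH responder. The bias on iPTH runs in the drug's favour.

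Its size is about 4.2 points per affected child if the standard-of-care set has 24. The number of such children is unknown and may be zero, because the documents give no procedure rate. The iPTH values in the working are assumptions, and they illustrate parathyroidectomy. The documents do not show how far iPTH moves within days of a transplant.

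Two stronger readings are not supported. A reader might infer that the responder rates are materially inflated; without a procedure rate, that cannot be said. A reader might also infer that parathyroidectomy has to count as treatment failure. The documents list it beside transplant as a protocol-specified reason to stop treatment and do not call it failure. Scoring it as non-response is a choice of estimand. Applied to any procedure before the window closes, it could fail a child with valid responses who completes treatment at about day 197 and has surgery on day 205, because the week 28 window runs to day 211.

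**What to change.** Add to SAP 10.1: laboratory values collected after a parathyroidectomy or renal transplant are excluded from all efficacy analyses, whatever the interval since the last dose. Add to SAP 10.6.1 that its existing missing-data rules then apply to the remaining pre-procedure values. The same cut carries through to the sensitivity analyses.

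Counting parathyroidectomy as non-response can be an optional sensitivity analysis, limited to procedures during treatment. It is not part of the required change.

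This is a cheap improvement: two sentences and one date condition in the programming, with a check that procedure dates reach the analysis data. The downside is a few lost values and a responder rate that may be slightly lower. It concerns analysis only; nothing in treatment or follow-up changes.
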